8.2 SAFETY ASSESSMENTS

Planned time points for all safety assessments are provided in the SoA (Section 1.3).

8.2.1 Physical examinations

A physical examination will be performed at the time points specified in the SoA (Section 1.3).

• A complete physical examination will include, at a minimum, assessments of the general appearance, head and neck, abdomen, lymph nodes, skin, cardiovascular system, respiratory system, musculoskeletal system, and neurological examination by the Treating Investigator. Height (at screening) and weight will also be measured and recorded. Further details will be provided in the Study Manual.

- A brief physical examination will include, at a minimum, assessments of the skin, lungs, cardiovascular system, neurological examination, and abdomen (liver and spleen).
- Investigators should pay special attention to clinical signs related to previous serious illnesses.
- Any clinically significant new finding or worsening of previous finding should be reported as an AE, per Investigator's judgement.

The extent of the physical examination can be broadened at the discretion of the Treating Investigator in order to evaluate AEs or abnormal clinical laboratory test values.

8.2.2 Vital signs

- Body temperature, heart rate, and blood pressure will be assessed.
- Blood pressure and pulse measurements will be assessed with the participant in a supine or sitting position with a completely automated device. Manual techniques will be used only if an automated device is not available.
- Blood pressure and pulse measurements should be preceded by at least 5 minutes of rest for the participant in a quiet setting without distractions (eg, television, cell phones).
- Vital signs (to be taken before blood collection for laboratory tests) will consist of 1 heart rate and 3 blood pressure measurements (3 consecutive blood pressure readings will be recorded at intervals of at least 1 minute).

8.2.3 Electrocardiograms

- 12-lead ECG will be obtained as outlined in the SoA (see Section 1.3) using an ECG machine that automatically calculates the heart rate and measures PR, QRS, QT, and QTcF intervals. Refer to Section 7 for QTcF withdrawal criteria. In case the ECG machine does not automatically calculate QTcF, manual calculation using nomogram or automatic website calculator (eg, https://reference.medscape.com/calculator/48/ecg-corrected-qt) is acceptable
- ECG and 30 second rhythm strips will be obtained locally. Further details will be included in the Study Manual.

8.2.4 Clinical safety laboratory assessments

- See Appendix 2 (Section 10.2) for the list of clinical laboratory tests to be performed. Per the SoA, serology tests for hepatitis B and C will be performed during screening; testing for other infectious disease should be performed during screening if required locally.
- The Treating Investigator may solicit emergency local laboratory data in case of emergent safety events to allow for appropriate treatment decisions. All clinically relevant solicited emergency local laboratory data will be recorded in the eCRF.

- The Treating Investigator must review the laboratory report, document this review, and record any clinically relevant changes occurring during the study in the AE section of the eCRF. The laboratory reports must be filed with the source documents. Clinically significant abnormal laboratory findings are those which are not associated with the underlying disease, unless judged by the Investigator to be more severe than expected for the participant's condition.
- All laboratory tests with values considered clinically significantly abnormal during participation in the study or within 30 days after the last dose of study intervention should be repeated until the values return to normal or baseline or are no longer considered clinically significant by the Investigator.
 - If abnormal laboratory values do not return to normal/baseline within a period of time judged reasonable by the Investigator, the etiology should be identified and the Sponsor notified.
- All protocol-required laboratory assessments, as defined in Appendix 2 (Section 10.2), must be conducted in accordance with the laboratory manual and the SoA. In the event the laboratory assessments in Appendix 6 (Section 10.6) indicate discontinuation of IMP, temporary discontinuation should be considered unless otherwise specified.
 - If laboratory values from non-protocol specified laboratory assessments performed at the institution's local laboratory require a change in participant management or are considered clinically significant by the Investigator (eg, SAE or AE or dose modification), then the results must be recorded in the eCRF.

8.2.5 Suicidal ideation and behavior risk monitoring

SAR442168 crosses the blood-brain barrier. Assessment of suicidal ideation and behavior as well as treatment-emergent suicidal ideation and behavior will be monitored during Study EFC16645 using the C-SSRS. For safety reasons, C-SSRS will be administered throughout the study by the Treating Investigator or delegated to an individual who is certified for to administer the scale. Study drug administration must be interrupted if a participant scores "yes" on items 4 or 5 of the Suicidal Ideation Section of the C-SSRS, or "yes" on any item of the Suicidal Behavior Section. A psychiatrist will be consulted and decide whether the study drug can be restarted and if any additional risk mitigation strategies are required (eg, increased monitoring, antidepressant administration).

8.3 ADVERSE EVENTS AND SERIOUS ADVERSE EVENTS

The definitions of an AE or SAE can be found in Appendix 3 (Section 10.3).

AEs will be reported by the participant (or, when appropriate, by a caregiver, surrogate, or the participant's legally authorized representative).

The Investigator and any qualified designees are responsible for detecting, documenting, and recording events that meet the definition of an AE or SAE and remain responsible for following up AEs that are serious, considered related to the study intervention or study procedures, or that caused the participant to discontinue the study intervention (see Section 7).

8.3.1 Time period and frequency for collecting AE and SAE information

All SAEs will be collected from the signing of the ICF until the follow-up visit/EOS visit at the time points specified in the SoA (Section 1.3).

All AE will be collected from the signing of the ICF at the time points specified in the SoA (Section 1.3).

All SAEs and AESI will be recorded and reported to the Sponsor or designee immediately and under no circumstance should this exceed 24 hours, as indicated in Appendix 3 (Section 10.3). The Investigator will submit any updated SAE data to the Sponsor within 24 hours of it being available.

Investigators are not obligated to actively seek AE or SAE after conclusion of the study participation. However, if the Investigator learns of any SAE, including a death, at any time after a participant has been discharged from the study, and he/she considers the event to be reasonably related to the study intervention or study participation, the Investigator must promptly notify the Sponsor.

8.3.2 Method of detecting AEs and SAEs

The method of recording, evaluating, and assessing causality of AE and SAE and the procedures for completing and transmitting SAE reports are provided in Appendix 3 (Section 10.3).

Care will be taken not to introduce bias when detecting AEs and/or SAEs. Open-ended and non-leading verbal questioning of the participant is the preferred method to inquire about AE occurrences.

8.3.3 Follow-up of AEs and SAEs

After the initial AE/AESI/SAE report, the Investigator is required to proactively follow each participant at subsequent visits/contacts. At the pre-specified study end-date, all SAEs, and AESIs (as defined in Section 8.3.9), will be followed until resolution, stabilization, the event is otherwise explained, or the participant is lost to follow up (as defined in Section 7.3). Further information on follow-up procedures is provided in Appendix 3 (Section 10.3).

8.3.4 Regulatory reporting requirements for SAEs

- Prompt notification by the Investigator to the Sponsor of an SAE is essential so that legal obligations and ethical responsibilities towards the safety of participants and the safety of a study intervention under clinical investigation are met.
- The Sponsor has a legal responsibility to notify both the local regulatory authority and other regulatory agencies about the safety of a study intervention under clinical investigation. The Sponsor will comply with country-specific regulatory requirements relating to safety reporting to the regulatory authority, Institutional Review Boards (IRB)/Independent Ethics Committees (IEC), and Investigators.

- Reporting of suspected unexpected serious adverse reactions (SUSARs) will be in accordance with Directive 2001/20/EC or as per national regulatory requirements in participating countries. SUSARs are reported to regulatory authorities, Investigators, and IRBs/IECs as follows:
 - For SUSARs that are life-threatening or result in death, reporting is no later than 7 days after first knowledge by the Sponsor, with all relevant follow-up information subsequently reported within an additional 8 days,
 - For SUSARs, other than those that are life-threatening or result in death, reporting is no later than 15 days after first knowledge by the Sponsor.
- Adverse events that are considered expected will be specified in the reference safety information (see the Investigator's brochure [IB]).
- An Investigator who receives an Investigator safety report describing an SAE, SUSAR or any other specific safety information (eg, summary or listing of SAEs) from the Sponsor will review and then file it along with the IB and will notify the IRB/IEC, if appropriate according to local requirements. It is the responsibility of the Sponsor to assess whether an event meets the criteria for a SUSAR, and therefore, is expedited to regulatory authorities.

8.3.5 Pregnancy

Details of all pregnancies in female participants and female partners of male participants will be collected after the start of study intervention and until the follow-up/EOS Visit (Note: A separate informed consent must be obtained for data collection from partners of male participants). The participant will be followed to determine the outcome of the pregnancy and should be followed even after the end of the study (See Appendix 4 [Section 10.4]).

- If a pregnancy is reported, the Investigator should inform the Sponsor within 24 hours of learning of the pregnancy and should follow the procedures outlined in Appendix 4 (Section 10.4).
- A negative pregnancy test is required prior to starting a treatment course. In the event that a pregnancy is confirmed during a course of treatment, the IMP should be discontinued.
- A pregnancy will qualify as an SAE only if it fulfills at least 1 of the seriousness criteria (see Appendix 3 [Section 10.3]).
- Abnormal pregnancy outcomes (eg, spontaneous abortion, fetal death, stillbirth, congenital anomalies, and ectopic pregnancy) are considered SAEs.
- AEs that occur to study participants who become pregnant are to be reported according to the relevant portion of Appendix 3 (Section 10.3).

8.3.6 Cardiovascular and death events

Atrial fibrillation and atrial flutter are AESIs in this study and subject to expedited reporting to the Sponsor. All other cardiovascular events will be reported per standard safety reporting and safety oversight practices (including data review by DMC).

Amended Clinical Trial Protocol 12 SAR442168-EFC16645 - tolebrutinib 20-Dec-2023 Version number: 1

Death events will be reported per standard SAE reporting rules. Every effort will be made to clarify the cause of death and to report the diagnosis of the fatal event as an SAE.

8.3.7 Multiple sclerosis relapse reporting

Multiple sclerosis relapses, determined from the evaluations described in Section 8.1.3, as with all efficacy endpoints, will be exempt from being reported as AEs except when they meet the definition of an SAE or are medically severe or medically unexpected. Hospitalization for MS relapse, if done routinely at the site (eg, for high dose IV methylprednisolone), will not be considered as a seriousness criterion for this study.

Multiple sclerosis relapses will be collected on the eCRF and be analyzed as part of the efficacy analysis. Other worsening of neurological symptoms that do not meet the definition of MS relapse will be reported as AEs according to general safety reporting rules.

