10.3.1 Definition of AE

AE definition

- An AE is any untoward medical occurrence in a patient or clinical study participant, temporally associated with the use of study intervention, whether or not considered related to the study intervention.
- NOTE: An AE can therefore be any unfavorable and unintended sign (including an abnormal laboratory finding), symptom, or disease (new or exacerbated) temporally associated with the use of study intervention.

Events meeting the AE definition

- Any abnormal laboratory test results (hematology, clinical chemistry, or urinalysis) or other safety assessments (eg, ECG, radiological scans, vital signs measurements), including those that worsen from baseline, considered clinically significant in the medical and scientific judgment of the Investigator (ie, not related to progression of underlying disease), eg:
 - Symptomatic and/or
 - Requiring either corrective treatment or consultation, and/or
 - Leading to IMP discontinuation or modification of dosing, and/or
 - Fulfilling a seriousness criterion, and/or
 - Defined as an AESI.
- Exacerbation of a chronic or intermittent pre-existing condition including either an increase in frequency and/or intensity of the condition.
- New conditions detected or diagnosed after study intervention administration even though it may have been present before the start of the study.
- Signs, symptoms, or the clinical sequelae of a suspected drug-drug interaction.
- Signs, symptoms, or the clinical sequelae of a suspected overdose of either study intervention or a concomitant medication.
- "Lack of efficacy" or "failure of expected pharmacological action" per se will not be reported as an AE or SAE. Such instances will be captured in the efficacy assessments. However, the signs, symptoms, and/or clinical sequelae resulting from lack of efficacy will be reported as AE or SAE if they fulfil the definition of an AE or SAE.

Events NOT meeting the AE definition

- Any clinically significant abnormal laboratory findings or other abnormal safety assessments which are associated with the underlying disease, unless judged by the Investigator to be more severe than expected for the participant's condition.
- The disease/disorder being studied or expected progression, signs, or symptoms of the disease/disorder being studied, unless more severe than expected for the participant's condition.

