10.3.2 Definition of SAE

If an event is not an AE per definition above, then it cannot be an SAE even if serious conditions are met (eg, hospitalization for signs/symptoms of the disease under study, death due to progression of disease).

An SAE is defined as any untoward medical occurrence that, at any dose:

- A) Results in death
- B) Is life-threatening

The term "life-threatening" in the definition of "serious" refers to an event in which the participant was at risk of death at the time of the event. It does not refer to an event, which hypothetically might have caused death, if it were more severe.

C) Requires inpatient hospitalization or prolongation of existing hospitalization

In general, hospitalization signifies that the participant has been detained (usually involving at least an overnight stay) at the hospital or emergency ward for observation and/or treatment that would not have been appropriate in the physician's office or outpatient setting. Complications that occur during hospitalization are AEs. If a complication prolongs hospitalization or fulfills any other serious criteria, the event is serious. When in doubt as to whether "hospitalization" occurred or was necessary, the AE should be considered serious.

Hospitalization for elective treatment of a pre-existing condition that did not worsen from baseline is not considered an AE.

- D) Results in persistent disability/incapacity
 - The term disability means a substantial disruption of a person's ability to conduct normal life functions.
 - This definition is not intended to include experiences of relatively minor medical significance such as uncomplicated headache, nausea, vomiting, diarrhea, influenza, and accidental trauma (eg, sprained ankle) which may interfere with or prevent everyday life functions but do not constitute a substantial disruption.
- E) Is a congenital anomaly/birth defect
- F) Other situations:
 - Medical or scientific judgment should be exercised in deciding whether SAE reporting is appropriate in other situations such as important medical events that may not be immediately life-threatening or result in death or hospitalization but may jeopardize the participant or may require medical or surgical intervention to prevent one of the other outcomes listed in the above definition. These events should usually be considered serious.

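### Protocol 8.3.7 and Appendix 3 do not settle whether gradual MS progression is an AE, and the SAP has no display that separates progression from other AEs

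*Protocol*

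**What the plan says.** Four parts of the protocol bear on whether gradual neurological worsening is an AE.

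- **Section 8.3.7, first sentence.** Relapses, "as with all efficacy endpoints, will be exempt from being reported as AEs except when they meet the definition of an SAE", or when they are medically severe or unexpected.
- **Section 8.3.7, last sentence.** "Other worsening of neurological symptoms that do not meet the definition of MS relapse will be reported as AEs"; the sentence ends by referring to the general safety reporting rules.
- **Appendix 3, Section 10.3.1.** Among events not meeting the AE definition: "The disease/disorder being studied or expected progression, signs, or symptoms of the disease/disorder being studied, unless more severe than expected". The same section says lack of efficacy is not itself an AE, but that its signs, symptoms and "clinical sequelae resulting from lack of efficacy will be reported as AE or SAE if they fulfil the definition of an AE or SAE".
- **Appendix 3, Section 10.3.2.** Anything outside the AE definition cannot be an SAE, whatever seriousness criterion it meets. Among the criteria is "Results in persistent disability/incapacity".

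Protocol Section 8.2.1 adds another route: new or worsened examination findings are reported as AEs when clinically significant in the Investigator's judgement. Both types of examination include a neurological part.

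SAP Section 3.6.2 counts every AE that develops, worsens or becomes serious in the double-blind treatment-emergent period. It has no rule for progression terms. SAP Section 5.5 adds relative-risk and risk-difference displays and lists of preferred terms that are more frequent on tolebrutinib than on placebo.

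**The concern.** The population was chosen for having progression without relapse, so the last sentence of Section 8.3.7 covers what is often the main expected clinical event. Taken alone, it tells a site to record gradual gait worsening as an AE; Appendix 3 tells the site not to. The reference to general reporting rules can mean either how to file the report or that Appendix 3 decides whether there is anything to report.

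The exemption for efficacy endpoints does not close the gap. Treating Investigators, who collect safety events, do not see EDSS scores after screening and are alerted only at 6-month CDP (Protocol Sections 6.4 and 8.1.1). When a participant first reports worsening, the Treating Investigator cannot know whether it will become an endpoint. Section 8.1.3.2 requires participants to report worsening symptoms at once, so these reports will arise regularly.

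At stake is the aggregate safety comparison. If efficacy failures are counted as AEs, a drug that delays progression lowers its own AE rate relative to placebo, to an extent that depends on how sites read the text.

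**Working it through.** **Inputs.** From Protocol Section 9.2 and SAP Section 4: 2-year placebo event rate 23.6%; 30% risk reduction (HR 0.70); 2:1 allocation; up to 1290 randomized; 10% annual discontinuation; 24 months of enrollment plus 24 months of follow-up for the last participant; 288 events for 80% power. The share of 6-month CDP that sites record as AEs is not in the documents and is assumed to lie anywhere from 0% to 100%.

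**The plan's own figure.** Schoenfeld events = (1.960 + 0.842)² / [(2/3)(1/3)(ln 0.70)²] = 278, and 288 events give 81.4% power. The stated 288 is slightly conservative, which has no bearing on this point.

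**Cumulative 6-month CDP, constant hazards.**

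- Placebo hazard: −ln(1 − 0.236)/2 = 0.1346 per year.
- Tolebrutinib hazard: 0.70 × 0.1346 = 0.0942 per year.
- Dropout hazard: −ln(0.90) = 0.1054 per year.
- Probability of an event by time u: λ/(λ+δ) × [1 − exp(−(λ+δ)u)], averaged over u uniform on 2 to 4 years.
- Placebo: 0.561 × (1 − 0.4915) = 28.5%.
- Tolebrutinib: 0.472 × (1 − 0.5532) = 21.1%.
- Difference: 7.4 points. Expected participants with an event: 430 × 0.285 ≈ 123 and 860 × 0.211 ≈ 181, about 304 in all.

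With the documents' 28-day month, the same model gives 26.9% and 19.8% and 286 events. With 1100 participants and at least 30 months of follow-up it gives 31.6% and 23.6% and 289 events. Both totals are close to 288. The full-recording difference is about 7.1 and 8.1 points respectively.

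**Participants with a recorded progression AE (N = 1290, calendar months).**

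| Share of CDP recorded | Placebo | Tolebrutinib | Difference (points) |
|---|---|---|---|
| 10% | 2.9% | 2.1% | 0.7 |
| 25% | 7.1% | 5.3% | 1.9 |
| 50% | 14.3% | 10.5% | 3.7 |
| 100% | 28.5% | 21.1% | 7.4 |

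**Dependence on the drug effect (100% recorded).** The placebo-minus-tolebrutinib difference is 7.4 points at HR 0.70, 3.6 at HR 0.85, 0 at HR 1.0 and −3.4 at HR 1.15.

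**Why these are upper bounds for any TEAE.** A participant with another TEAE is already counted. CDP arising more than 10 days after the last dose falls outside the treatment-emergent period. Worsening that is never confirmed is not modelled.

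**The case against.** The strongest reply is that there is no contradiction. The last sentence of Section 8.3.7 defers to the general rules, Section 8.3 places the AE definitions in Appendix 3, and Appendix 3 excludes expected progression. The sentence also sits under relapse reporting, so it may be meant only for episodes worked up as possible relapse and found to be something else, such as intercurrent illness or possible PML. Recording those has a clear safety purpose. This is a reasonable reading, but the text does not require it. The sentence carries no exception for progression, and the general rules themselves point both ways through the lack-of-efficacy text and Section 8.2.1.

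Three further replies stand and limit the point.

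- **SAEs.** A reader might infer that progression enters the SAE tables directly as persistent disability. Section 10.3.2 blocks this: the event must first be accepted as an AE, for example because it is more severe than expected. The exception in Section 8.3.7 for endpoints that meet the SAE definition is circular with that rule, but it does not override it.
- **Masked toxicity.** A reader might infer that real harm would be hidden. The documents do not support this. Tables by system organ class and preferred term keep progression terms on their own rows. The identified risk, liver injury, has separate ALT, PCSA and Kaplan-Meier analyses (SAP Sections 3.6.2 and 3.6.3.1). The exposure is in the aggregate overview lines and the placebo-comparison displays.
- **Timing.** Randomization began in October 2020 and the current SAP is dated April 2024. A new reporting rule cannot reclassify what sites have already entered.

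**Conclusion.** The point holds as an unreconciled reporting rule with no matching safeguard in the SAP. Sites can differ on whether gradual progression is an AE, and if some record it, aggregate TEAE lines and the SAP Section 5.5 comparisons mix efficacy failure with safety.

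The documents cannot fix the size. The 0.7 to 7.4 points for shares of 10% to 100% rest on the planning event rate, HR 0.70, constant hazards and 10% annual dropout. It would be wrong to infer that placebo rates must rise relative to tolebrutinib: both arms would rise, the gap requires that the drug delays progression, and under 2:1 allocation the larger count would be on tolebrutinib (about 181 against 123 at full recording). No efficacy test, type I error, power or sample size is involved, and safety analyses are descriptive. The change is worth making because it is cheap and keeps the aggregate safety comparison interpretable, but the trial's conclusions do not depend on it.

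**What to change.** **SAP (the main change).** Prespecify, before unblinding, a list of preferred terms for MS progression or worsening. Show the TEAE and SAE overviews in Section 3.6.2 and the relative-risk and risk-difference displays in Section 5.5 with and without those terms. This works whichever way sites have read the protocol.

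**Protocol.** Reconcile the last sentence of Section 8.3.7 with its first sentence and with Appendix 3, so that one rule applies. Keep AE reporting for worsening that is more severe than expected or has another suspected cause. Send sites a short reminder.

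**Cost.** One clarified sentence and one extra set of tables. AEs already collected under the existing protocol text will remain a mixture of both readings, which is why the SAP display matters more than the wording change.
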